8. SAFETY AND TOLERABILITY

8.1. Adverse Event Preferred Term and Body/Organ System Summary Tables

TEAEs and serious TEAE will be summarized. See [Section 5.5.10.2](#) for the definitions of TEAEs and serious TEAEs.

The Medical Dictionary for Regulatory Activities (MedDRA) will be used to classify AEs by system organ class and preferred term. The severity of adverse events will be evaluated using the National Cancer Institute Common Terminology Criteria for Adverse Events (NCI-CTCAE) Version 4.0. Coding will be performed using version 20.0 of the MedDRA coding dictionary.

8.1.1. Summaries of Adverse Event Incidence Rates for All Patients

The number and percentage of patients with TEAEs will be summarized by system organ class, preferred term, dose level and overall, riluzole and edaravone use status at baseline, and will be further tabulated by CTCAE grade or relationship to study drug. For a patient with a particular

TEAE that were reported more than once within a particular system organ class or preferred term, the patient will be counted only once in that category using the most severe occurrence or closest relationship to the study drug. Listings of all AEs by patient will also be presented.

8.1.2. Summaries of Adverse Incidence Rates for Serious Adverse Events, Adverse Event Dropouts, and Death

SAEs and AEs leading to treatment discontinuation or death will also be summarized by system organ class, preferred term, dose level and overall, and riluzole and edaravone use status at baseline. Listings will be presented for patients who died and/or experienced serious AEs and for patients who discontinued due to TEAEs.

8.2. Total Duration of Therapy, Average Daily Dose, Maximum Daily Dose, Final Daily Dose of Study Medication, and Compliance

The duration and exposure of study drug will be summarized by dose level and overall, and riluzole and edaravone use status at baseline for the safety analysis set. The duration will be calculated as the difference between the study day of the first dose and the last dose plus one day. The exposure will be calculated as the total dosage in mg. Patient listing with date, day and time of dose, actual/average daily dose, reason for incorrect dose and dose interruption will be presented.

8.3. Concomitant and Other Medications

Concomitant medications reported on the eCRF will be summarized for the safety analysis set. See [Section 5.5.10.4](#) for the definition of concomitant medications. Medications with a start date that is 28 days after the last dose of the study drug will be excluded from the summary. The World Health Organization Drug dictionary will be used to classify medications by therapeutic class (ATC Class 3) and preferred name. If ATC Class 3 is not available, ATC Class 2 will be used in the summary. Coding will be performed using WHO Drug Dictionary Enhanced with Herbal Dictionary, B2, March 2017.

The number and percentage of patients who received concomitant medication will be summarized by dose level, therapeutic class and preferred term (using ATC Class Level III). Multiple drug usage by a patient will be counted only once in each category.

CYP3A4 strong inhibitors that should be avoided from 7 days before the start of dosing through the last day of dosing. CYP3A4 strong inducers that should be avoided from 14 days before the start of dosing through the last day of dosing. OCT1/OCT2 substrates that should be avoided from 7 days before the start of dosing or should be used with caution during the trial. Patients who take CYP3A4 strong inhibitors, CYP3A4 strong inducers, or OCT1/OCT2 substrates prior or during the study treatment will be listed.

In addition, a listing of concomitant medication with start/stop date, days relative to the start of therapy, dose / unit / route / frequency, indication and purpose of all medications taken from screening through the end of study will be provided.

8.4. Routine Laboratory Data

Clinical laboratory evaluations, including hematology, serum chemistry, and urinalysis as detailed in the protocol, will be collected at the Screening, Day 1, Week 2, Week 4, Week 12 and Follow-Up Visits. Descriptive statistics of assessment value and change from baseline of laboratory parameters will be presented at each assessment time point by dose level and overall.

The number and percentage of patients who had normal or missing laboratory values at baseline and abnormal laboratory values post baseline will be presented by dose level and overall. The lower limit of normal (LLN) and upper limit of normal (ULN) provided by the laboratories will be used as the criteria for abnormality. For each parameter, the denominator of the percentage will include patients with normal or missing assessments at baseline, and with at least one assessment post baseline. The numerator of the percentage will include patients who had at least one abnormal assessment post baseline among the patients that were counted in the denominator. Assessment collected at an unscheduled visit or the Follow-up Visit will also be included in the summary.

Shift of clinical laboratory results in NCI-CTCAE grade from baseline grade to the maximum post baseline grade will be presented for selected laboratory parameters. Clinical laboratory values will be also listed. Values outside the Laboratory's normal ranges and potentially clinically significant abnormal values will be flagged.

Hy's law ([Temple 2006](#)) will be used to evaluate drug induced liver injury (DILI); patients with ALT or AST elevations $> 3 \times$ ULN and total bilirubin elevations $> 2 \times$ ULN will be marked on a scatter plot. Elevations of ALT or AST to $5 \times$, $10 \times$ or $20 \times$ ULN will also be plotted.

Clinical laboratory results from patients with eGFR decline of 1) greater than 25%, 2) below 60, 3) greater than 25% and below 60, and 4) greater than 25% or below 60 will be summarized and listed. Time-to-event analysis will be performed for eGFR decline of greater than 25% using proportional hazard Cox regression model with the following model terms: riluzole and edaravone use status at baseline, age, sex, BMI and baseline eGRF values. Kaplan-Meier method will be used to summarize the time to eGFR decline of greater than 25% where the median of the time to event, 95% CIs of the median, Q1, Q3, and range will be provided. In addition, the correlation between eGFR level change from baseline and C_{trough} of reldesemtiv and its metabolites will be examined. Similar method as described in [Section 9.2](#) will be used for the analysis.

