4.2. Exclusion Criteria

Any of the following will exclude potential patients from the study:

1. At the time of screening, any use of non-invasive ventilation, e.g. continuous positive airway pressure, noninvasive bi-level positive airway pressure or noninvasive volume ventilation, for any portion of the day, or mechanical ventilation via tracheostomy, or on any form of oxygen supplementation
2. Neurological impairment due to a condition other than ALS
3. Presence at screening of any medically significant cardiac, pulmonary, gastrointestinal, musculoskeletal, or psychiatric illness that might interfere with the patient's ability to comply with study procedures or that might confound the interpretation of clinical safety or efficacy data, including, but not limited to:
 - a. A pulse <40 or >100 bpm; mean systolic blood pressure >180 mm Hg; mean diastolic blood pressure >100 mm Hg (based on measurements taken after rest for 3 minutes) that persist on 3 successive measurements taken at least 2 minutes apart.
 - b. Clinically significant ECG abnormalities that require medical attention (i.e., persistent atrioventricular conduction block >first degree, or acute myocardial ischemic changes)
 - c. New York Heart Association Class II or greater congestive heart failure
 - d. Chronic obstructive pulmonary disease or asthma requiring daily use of bronchodilator medications
 - e. Gastrointestinal disorder that is likely to impair absorption of study drug from the gastrointestinal tract
 - f. ALT or aspartate aminotransferase (AST) greater than or equal to 3-times the upper limit of normal (ULN) or has total bilirubin (TBL) greater than or equal to 2-times the ULN at screening. These assessments may be repeated at the Investigator's discretion (within the screening window).
 - g. Poorly controlled or brittle diabetes mellitus
 - h. Amputation of a limb
 - i. Cognitive impairment, related to ALS or otherwise, sufficient to impair the patient's ability to understand and/or comply with study procedures and provide informed consent

- j. Cancer with metastatic potential (other than basal cell carcinoma, carcinoma in situ of the cervix, or squamous cell carcinoma of the skin excised with clean margins) diagnosed and treated within the last five years
 - k. Any other condition, impairment or social circumstance that, in the opinion of the Investigator, would render the patient not suitable to participate in the study

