8.4.5.4. Clinical Laboratory Parameters

For each laboratory parameter, the number and percentage of subjects with alert values or values outside the normal range during the study will be tabulated. All laboratory evaluations identified as outside the normal range or as alerts by the central laboratory will be listed. The value and change from baseline in continuous laboratory parameters will be summarized at each scheduled visit where laboratory measurements are taken.

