8.4.5.5. Vital Signs

For each measurement of heart rate, blood pressure, respiratory rate, and BMI, the number and percentage of subjects with clinically relevant abnormalities during the study will be tabulated. All measurements identified as clinically relevant abnormalities will be listed. The value and change from baseline in heart rate, blood pressure, respiratory rate and BMI will be summarized at each scheduled visit where vital signs are taken.

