8.4.5.6. ECGs

For each ECG measurement, the number and percentage of subjects with clinically relevant abnormalities during the study will be tabulated. ECG measurements identified as clinically relevant abnormalities will be listed. The value and change from baseline in ECG measurements will be summarized at each scheduled visit where measurements are taken.

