8.5. Vital Signs

Vital signs, which include blood pressure, heart rate and respiratory rate (measured after the patient has been resting for at least 3 minutes), height, weight and BMI will be obtained at the Screening, Day 1, Week 2, Week 4, Week 8, Week 12 and Follow-Up Visits. Descriptive statistics of absolute values and changes from baseline of vital sign parameters will be presented at each assessment time point by dose level and overall.

The number and percentage of patients who had normal or missing values at baseline and Potentially Clinically Significant (PCS) values post baseline will be presented by dose level and overall. The PCS criteria are specified in [Table 6](#). For each parameter, the denominator of the percentage will include patients with non-PCS or missing assessments at baseline, and with at

least one assessment post baseline. The numerator of the percentage will include patients who had at least one PCS assessment post baseline among the patients that were counted in the denominator. Assessment collected at an unscheduled visit or the Follow-up Visit will also be included in the summary.

Oral temperature will be taken at Screening and will be presented in a listing. Individual vital signs will be listed with dose level, patient ID, and assessment time. Values outside the normal ranges will be flagged.

Table 6: Criteria of Potentially Clinically Significant (PCS) Vital Signs

Vital Sign Parameter	Flag	Criteria
Systolic Blood Pressure (mmHg)	High	≥160 mmHg
	Low	≤80 mmHg
Diastolic Blood Pressure (mmHg)	High	≥100 mmHg
	Low	≤ 50 mmHg
Respiration Rate (Breaths per minute)	High	>18 bpm
	Low	<8 bpm
Pulse (bpm)	High	≥120 bpm
	Low	≤50 bpm
Weight (kg)	Clinically Significant	≥5% reduction from baseline
Temperature (°C)	High	≥ 38 °C
	Low	< 35 °C

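### SAP 8.4 to 8.6 replace the protocol's all-subject abnormality tables with baseline-restricted ones and omit the laboratory alert count, and SAP 12 declares neither change

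*SAP*

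**What the plan says.** The two documents define the same safety tables differently.

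- **Laboratory.** Protocol 8.4.5.4 states that for each parameter "the number and percentage of subjects with alert values or values outside the normal range during the study will be tabulated". It adds a listing: "All laboratory evaluations identified as outside the normal range or as alerts by the central laboratory will be listed". SAP 8.4 states: "The number and percentage of patients who had normal or missing laboratory values at baseline and abnormal laboratory values post baseline will be presented". The SAP criterion is the laboratory's lower or upper limit of normal (LLN, ULN). Alerts are not mentioned in that section.
- **Vital signs.** Protocol 8.4.5.5 states that "the number and percentage of subjects with clinically relevant abnormalities during the study will be tabulated". SAP 8.5 introduces its table as covering patients normal or missing at baseline, but then specifies that "the denominator of the percentage will include patients with non-PCS or missing assessments at baseline".
- **ECG.** Protocol 8.4.5.6 states: "For each ECG measurement, the number and percentage of subjects with clinically relevant abnormalities during the study will be tabulated". SAP 8.6 uses the same restricted construction as SAP 8.5, with the same mismatch between normal and non-PCS.
- **Record of changes.** SAP 12, the section for departures from the protocol's analyses, reads only 'not available'.

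**The concern.** None of the three protocol tables conditions on baseline status. All three SAP tables do. A patient already abnormal (laboratory) or already PCS (vital signs, ECG) at baseline leaves both the numerator and the denominator for that parameter, whatever happens afterwards. A patient who enters with a systolic pressure of 165 mm Hg and reaches 210 is not in the blood-pressure table. A patient who enters at 20 breaths per minute and reaches 32 is not in the respiratory-rate table.

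Protocol 8.3.2 and SAP 2.2.5 both make clinically important changes in these assessments a safety endpoint, and Protocol 3.3 says the trial will guide dose selection for Phase 3. Following the SAP as written would leave out counts that the protocol requires. For some patients there would be no objective categorical summary of worsening by dose.

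**Working it through.** The documents state no figure on this point, so the check is a comparison of text followed by a labelled illustration.

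**1. The rules side by side**

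| Domain | Protocol | SAP | Who leaves the SAP table |
|---|---|---|---|
| Laboratory | Any alert or out-of-range value during the study | Out-of-range after baseline, among patients normal or missing at baseline | Anyone out of range at baseline for that parameter, in either direction |
| Laboratory alerts | Counted and listed | No count | Not applicable |
| Vital signs | Any clinically relevant abnormality during the study | PCS after baseline, among patients non-PCS or missing at baseline | Only patients already PCS |
| ECG | Any clinically relevant abnormality during the study | PCS after baseline, among patients non-PCS or missing at baseline | Only patients already PCS |

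The laboratory restriction ignores direction. A patient below the LLN at baseline and above the ULN later is removed as well.

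**2. Can such patients be enrolled?** Yes.

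- Inclusion criterion 8 admits out-of-range laboratory values that the investigator judges not clinically significant. Exclusion criterion 3f admits ALT or AST below 3 x ULN.
- Exclusion criterion 3a removes patients with "mean systolic blood pressure >180 mm Hg". SAP Table 6 sets PCS at 160 or more, so 160 to 180 mm Hg can enter and is already PCS.
- The same criterion admits a pulse of 40 to 100. PCS low is 50 or less, so 40 to 50 can enter and is already PCS.
- The entry criteria set no limit on respiratory rate. PCS high is above 18 breaths per minute.

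**3. What else in the SAP reaches these patients?**

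- Treatment-emergent adverse events include events that worsen after first dose (Protocol 8.4.5.2, SAP 5.5.10.2), and SAP 8.1.1 tabulates them by dose level and grade. Entry depends on the investigator judging the change clinically significant (Protocol 7.1.1).
- SAP 8.4 has a CTCAE shift to maximum post-baseline grade, for laboratory parameters that it calls selected but does not name.
- SAP 8.4 plots ALT, AST and bilirubin elevations, and analyses eGFR decline of more than 25% by Kaplan-Meier and Cox methods. None of these is limited to patients normal at baseline.
- Change from baseline by visit, and listings, cover all three domains.

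**4. What is left?** (a) Counts of laboratory alert values. (b) Laboratory parameters outside the unnamed selection, including low-to-high and high-to-low shifts. (c) Vital signs and ECG in patients already PCS at baseline, for whom no shift table is planned.

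**5. Illustration under assumed rates.** Planned size is about 445 at 1:1:1:1, so 445 / 4 = about 111 per arm. Let b be the share abnormal at baseline for a laboratory parameter, e the rate of new abnormality among the rest, and q the chance that a baseline-abnormal patient is also abnormal later. All three are assumptions.

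- Removed per arm = 111 x b. At b = 5% this is 5.6, and at b = 30% it is 33.3.
- SAP rate = e. Protocol rate = b x q + (1 - b) x e.
- With e = 10% and b = 5%: 0.05 x 0.50 + 0.95 x 0.10 = 12.0% at q = 50%, and 0.05 x 0.90 + 0.95 x 0.10 = 14.0% at q = 90%. The SAP table shows 10%.
- With e = 10% and b = 30%: 0.30 x 0.50 + 0.70 x 0.10 = 22.0%, and 0.30 x 0.90 + 0.70 x 0.10 = 34.0%. The SAP table again shows 10%.

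The two tables estimate different quantities. The difference is not a count of worsening, because the extra protocol cases include patients who are stable or improving.

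**The case against.** A reader might infer that worsening in any patient abnormal at baseline goes uncounted. The documents do not support that, for the reasons in step 3. For vital signs and ECG, moreover, only patients already PCS are removed: a QTc rising from 470 to 510 msec is counted, because PCS is above 500. PCS weight loss is defined relative to baseline, so nobody can be removed for it.

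It is also fair to say that the SAP table is a defensible choice. A new-onset table follows the same logic as treatment-emergent adverse events, while the protocol's count treats a patient stable at 165 mm Hg the same as one who reaches 210. This stands, and it is a reason to keep the SAP table. It does not explain why the protocol's count is dropped without a record.

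Protocol 8.7 says that changes in methods described in the SAP will be documented in the clinical study report, so SAP 12 is not the only place for a record. That softens the complaint. But SAP 12 exists for this purpose and lists nothing.

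Finally, the alerts that the protocol describes concern liver abnormalities (Appendix C), and SAP 8.4 plots the corresponding elevations and flags potentially clinically significant laboratory values in listings. This covers part of the ground. A plot or a flagged listing is still not the per-parameter count that Protocol 8.4.5.4 asks for, and the SAP's PCS criteria (Tables 6 and 7) are for vital signs and ECG only.

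**Conclusion.** The point holds as an undeclared difference between protocol and SAP with a limited gap in the safety summaries. The SAP narrows three protocol tables by baseline status, omits the laboratory alert count, and describes its vital-sign and ECG tables inconsistently (normal in one sentence, non-PCS in the next). The uncovered ground is the three items in step 4.

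The size cannot be stated. The documents give no baseline-abnormal rate for any parameter, and any percentage of worsening said to be missed would rest wholly on assumed rates. The illustration shows only that the protocol and SAP percentages can differ materially. Two wider readings should be avoided: that the SAP loses a safety signal altogether, and that alert values were planned for vital signs or ECG. In the protocol's analysis sections alerts are a laboratory item only.

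**What to change.** Keep the SAP 8.4 to 8.6 tables, labelled as new-onset tables, and add beside them:

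- the protocol's all-subject counts regardless of baseline, including patients with any post-baseline central-laboratory alert value and with any post-baseline PCS vital sign or ECG value;
- shift tables from baseline category to worst post-baseline category for vital signs and ECG, including QTc;
- direction-specific laboratory shifts (low, normal, high), for all parameters or for a list named in the SAP.

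Use one term, normal or non-PCS, consistently in SAP 8.5 and 8.6, and record the baseline restriction in SAP 12.

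The cost is SAP wording and a few extra tables from data already collected. The all-subject counts will include stable pre-existing abnormalities, so they should be read together with the shift tables.

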8.5. Vital Signs

Vital signs, which include blood pressure, heart rate and respiratory rate (measured after the patient has been resting for at least 3 minutes), height, weight and BMI will be obtained at the Screening, Day 1, Week 2, Week 4, Week 8, Week 12 and Follow-Up Visits. Descriptive statistics of absolute values and changes from baseline of vital sign parameters will be presented at each assessment time point by dose level and overall.

The number and percentage of patients who had normal or missing values at baseline and Potentially Clinically Significant (PCS) values post baseline will be presented by dose level and overall. The PCS criteria are specified in [Table 6](#). For each parameter, the denominator of the percentage will include patients with non-PCS or missing assessments at baseline, and with at

least one assessment post baseline. The numerator of the percentage will include patients who had at least one PCS assessment post baseline among the patients that were counted in the denominator. Assessment collected at an unscheduled visit or the Follow-up Visit will also be included in the summary.

Oral temperature will be taken at Screening and will be presented in a listing. Individual vital signs will be listed with dose level, patient ID, and assessment time. Values outside the normal ranges will be flagged.

Table 6: Criteria of Potentially Clinically Significant (PCS) Vital Signs

Vital Sign Parameter	Flag	Criteria
Systolic Blood Pressure (mmHg)	High	≥160 mmHg
	Low	≤80 mmHg
Diastolic Blood Pressure (mmHg)	High	≥100 mmHg
	Low	≤ 50 mmHg
Respiration Rate (Breaths per minute)	High	>18 bpm
	Low	<8 bpm
Pulse (bpm)	High	≥120 bpm
	Low	≤50 bpm
Weight (kg)	Clinically Significant	≥5% reduction from baseline
Temperature (°C)	High	≥ 38 °C
	Low	< 35 °C

8.6. Electrocardiogram

A 12-lead ECG, including ECG parameters of RR, PR, QRS, and QT intervals as well as significant findings will be obtained at Screening, Week 4 and Follow-Up Visits. Descriptive statistics of absolute value and change from baseline of ECG parameters (PR interval, RR interval, QRS duration, QT interval, QTc interval [Bazett’s and Fridericia’s], Ventricular Heart Rate) will be presented at each assessment time point by dose level and overall.

The number and percentage of patients who had normal or missing values at baseline and PCS values post baseline will be presented by dose level and overall. ECG parameters are regarded as PCS if the value meets the criterion shown in Table 7. For each parameter, the denominator of the percentage will include patients with non-PCS or missing assessments at baseline, and with at least one assessment post baseline. The numerator of the percentage will include patients who had at least one PCS assessment post baseline among the patients that were counted in the denominator. Assessment collected at an unscheduled visit or the Follow-up Visit will also be included in the summary.

Twelve-lead ECG parameters (PR interval, QRS duration, QT interval, QTc interval [Bazett’s and Fridericia’s], Ventricular Heart Rate, and RR interval), will be listed with dose level, patient ID, visit and assessment date and time. PCS ECG values will be flagged. ECG findings and interpretations will be listed as well.

Table 7: Criteria of Abnormal and PCS ECG Values

ECG Variable	Units	Upper Limit of Normal	PCS High Values
QRS Interval	msec	80	≥120
PR Interval	msec	200	≥240
QTcB Interval	msec	Males: 450 Females: 460	>500
QTcF Interval	msec	Males: 450 Females: 460	>500
QT Interval	msec	—	> 500
Ventricular Heart Rate	bpm	—	>100

